4.1.2. Baseline Definition

For the LTFU phase, baseline is latest non-missing pre-primary series dose assessment from ZOSTER-041 study.

For the revaccination active and follow-up phases, baseline is the latest pre-revaccination dose assessment with a non-missing result from ZOSTER-073.

To assess long-term follow-up duration and decline post primary vaccination series peak-response, 1 month post-dose 2 of primary vaccination in ZOSTER-041 will be used.

Unless otherwise stated, if baseline data is missing, no derivation will be performed, and baseline will be set to missing.

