- Listing of subjects with biopsy-proven allograft rejection from Dose 1 of revaccination (study Month 24) up to study end will be provided. For subjects with an episode of biopsy-proven rejection, dates of biopsy-proven rejection episodes, treatment given (including dialysis), intensity, and rejection outcome will be included in the listing of renal transplant rejection history.
- Number and percentage of subjects with declining allograft function (following revaccination, HZ episode, and allograft rejection), as determined by serum creatinine measurements. Serum creatinine values will be summarized descriptively. See Section 4.5.3.1 for more details. Allograft dysfunction is defined as having a fold increase in serum creatinine of 1.2 or greater from the reference timepoint.

The listings will contain all events (HZ episodes, rejections) and columns will be included to indicate timing (up to Day 1, Before revaccination, et.)

CC1

CCI

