4.5. Other Safety Analyses

Safety analyses will be performed on the Enrolled Set for the LTFU phase. For the revaccinated subjects the Exposed Set for revaccination phase will be used. For non-revaccinated subjects, the Enrolled Set will be used to compare to revaccinated subjects past ZOSTER-073 Visit 3.

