4.5.3. Additional Safety Assessments

4.5.3.1. Laboratory Data

Allograft dysfunction will be assessed through serum creatinine measurements. The number and percentage with an increase from baseline (≥ 1.2 , ≥ 1.5 , ≥ 1.75 , ≥ 2 fold) in serum creatinine related to allograft rejection episodes, revaccination, and HZ episodes. will be tabulated based on whether the episode fell in the time frames outlined in Section [4.3.2.1](#) and Section [4.3.2.2](#)

See Section 6.2.3 for definitions of baseline and handling post-baseline measurements related to rejection episodes, revaccination, and HZ episodes.

A listing of raw serum creatinine measurements and their corresponding fold increase from baseline will be provided for each individual subject. Changes from baseline and percent changes from baseline will also be included for each subject, along with their primary and revaccination dates, if applicable.

Replacement kidney since ZOSTER-041 will also be listed.

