4.5.3.4. HZ Episodes

Suspected episodes of HZ will be identified via the HZ episode status eCRF.

Confirmed episodes of HZ will be identified via Polymerase Chain Reaction (PCR) test on HZ lesion sample.

The number of subjects with HZ episodes will be tabulated as follows:

- From ZOSTER-041 last visit (Month 13) to ZOSTER-073 Day 1
- From ZOSTER-073 Day 1 through ZOSTER-073 study Month 24
- From first revaccination up to study end

The number and percentage of non-revaccinated subjects reporting the occurrence of HZ episodes from visit 3 (Month 24) up to study end will also be presented.

All suspected and confirmed HZ episodes occurring between the end of ZOSTER-41 and ZOSTER-073 enrollment and occurring after ZOSTER-073 will be listed.

Immunosuppressive therapies before, during, and after the episode will be listed for subjects with HZ episodes in the concomitant medications listing.

GMCs of anti-gE antibody and CD4+T-cells secreting at least 2 activation markers in subjects who had suspected and/or confirmed HZ episodes will be displayed graphically. Values taken before and after the episode will be indicated using different colors and symbols in the figure.

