6.2.3. Multiple measurements at One Analysis Time Point

Baseline and post-baseline serum creatinine measures are computed as follows:

- For Allograft rejection:
 - The average of measurements 2 months prior to a biopsy-proven allograft rejection will be used as event baseline. If there are not 2 or more measurements in 2 months, then go back to 3 or 4 months prior to biopsy to have a minimum of 2 measurements.
 - The maximum of measurements taken up to 2 months after resolution of the biopsy-proven rejection, so that 2 or more additional post-rejection measurements are recorded, will be used to determine declining allograft function compared to baseline pre-allograft rejection measurements.
- For revaccination:
 - The average of measurements taken 3 months prior to first revaccination, Visit 3 (Month 24), will be used as pre-vaccination baseline. If there are not 3 or more measurements in 3 months, then go back to 4 or 5 months prior to revaccination to have a minimum of 3 measurements.
 - The maximum of measurements taken up to 3 months after last revaccination, Visit 5 (Month 26), so that 3 or more additional post-revaccination measurements are recorded, will be used to determine declining allograft function compared to pre-revaccination
- For episode of HZ cases:
 - The average of measurements taken 2 months prior to a HZ episode, will be used as event baseline. If there are not 2 or more measurements in 2 months, then go back to 3 or 4 months prior to HZ episode to have a minimum of 2 measurements.
 - The maximum of measurements taken up to 2 months after HZ episode rash resolution, so that 2 or more post-HZ resolution measurements are recorded, will be used to determine declining allograft function compared to pre-HZ episode.
- For non-revaccinated subjects:

- The mean of the available values before primary vaccination is used as baseline value.
- The maximum of the available values after Visit 3 Month 24 up to study end is used for calculating fold increase

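### SAP 6.2.3 gives creatinine fold increase a different baseline and time window in non-revaccinated and revaccinated subjects, so the ≥1.2-fold rates would not be comparable under SAP 4.5

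*SAP*

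**What the plan says.** SAP 6.2.3 holds two rules for creatinine around and after Visit 3.

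- **Revaccinated.** Baseline is the average over the 3 months before Visit 3, extended to 4 or 5 months if there are fewer than 3 values. The post-value is "The maximum of measurements taken up to 3 months after last revaccination, Visit 5 (Month 26").
- **Non-revaccinated.** "The mean of the available values before primary vaccination is used as baseline value". Then: "The maximum of the available values after Visit 3 Month 24 up to study end is used for calculating fold increase".

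One cut-off is stated for dysfunction: "Allograft dysfunction is defined as having a fold increase in serum creatinine of 1.2 or greater from the reference timepoint" (SAP 4.3.2.2, repeated in 4.3.2.1).

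On use, SAP 4.5 says of non-revaccinated subjects that "the Enrolled Set will be used to compare to revaccinated subjects past ZOSTER-073 Visit 3". Section 4.5.3.1 on creatinine sits under that heading, points to 6.2.3 for its baselines, and tabulates increases in "serum creatinine related to allograft rejection episodes, revaccination, and HZ episodes". It lists replacement kidneys received since ZOSTER-041 but gives no rule for them.

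**The concern.** A fold increase depends on how old the baseline is and how long one searches for the maximum. Here both differ by group while the cut-off is the same. If creatinine rises over the years, an old baseline carries that whole rise into the ratio. If more values fall in a longer window, their maximum is higher through variation alone. A baseline taken in a kidney since replaced (protocol 8.1.5 foresees this) does not describe the current graft at all.

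Allograft rejection is a stated theoretical concern for adjuvanted vaccines in this population (protocol 3.3.1). A reader who sets the two rates together could credit or blame revaccination for a difference produced by the derivation rules.

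**Working it through.** The plan states no rate for this quantity, so there is no figure to reproduce.

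**Step 1: baseline age at Visit 3.** Revaccinated: 0-3 (up to 5) months (SAP 6.2.3). Non-revaccinated: before primary vaccination, with Visit 3 about 6-7 years after the last primary dose (protocol Table 3).

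**Step 2: end of the post-value window, in days after Visit 3.** Three months are taken as 90 days.

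| Revaccinated, counted from | Table 4 | Table 8, upper limit |
|---|---|---|
| dose 2 (Visit 4) | 30+90=120 to 60+90=150 | 182+90=272 |
| Visit 5 | 30+30+90=150 to 60+48+90=198 | 182+90+90=362 |

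Non-revaccinated: Month 24 to Month 49, 25 × 30 = 750 days. This is nominal, because Table 8 lets Visit 7 move or be cancelled. Ratios: 750/120=6.3, 750/150=5.0, 750/198=3.8, 750/272=2.8, 750/362=2.1.

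**Step 3: effect on the ≥1.2-fold rate.** Within-subject CV, yearly drift and number of tests are not in the documents; all are assumptions. The same lognormal process was simulated in both groups, with no vaccine effect and 200,000 replicates per scenario. Ratio = max(k post-values) / mean(3 baseline values). Revaccinated: baseline 0-0.25 years before Visit 3, k=5 over 150 days. Non-revaccinated: baseline 6.25-6.75 years before Visit 3, k=2, 4, 12 or 25 over 750 days. Each cell gives % at CV 5/8/10%.

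| Drift per year | Revaccinated | Non-revacc., k=2 | k=4 | k=12 | k=25 |
|---|---|---|---|---|---|
| −1% | 0.3/9/20 | 0/0.5/2 | 0/0.9/4 | 0/3/11 | 0/5/20 |
| 0 | 0.4/10/21 | 0.1/4/10 | 0.3/8/18 | 0.9/20/38 | 1.7/32/55 |
| +1% | 0.4/11/22 | 6/21/29 | 11/35/46 | 25/62/74 | 40/78/87 |

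Each difference matters alone. At CV 8% and +1% per year, where the revaccinated rule gives about 11%, changing only the baseline gives 35.5%, and changing only the window (25 values) gives about 39%.

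**Step 4: one common rule.** With a pre-Visit 3 baseline and 4 values over about 4 months in both groups, the simulated rates agree: 8.2% against 8.1% at CV 8% without drift.

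**Step 5: higher cut-offs.** At ≥1.5 without drift, both groups stay at or below 0.5%. With 25 values and CV 10%, the non-revaccinated rate at ≥1.5 is 4.1% at +1% per year and 20.5% at +2%. At ≥1.75 and ≥2, no scenario run exceeded 0.5%.

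**Step 6: the window label.** SAP 6.2.3 and protocol 8.1.9 attach the last revaccination to Visit 5 (Month 26). Protocol Table 3 (footnote c) and SAP 1.2 put dose 2 at Visit 4 (Month 25). The endpoint (protocol Table 5, SAP 1.1) ends 3 months after the last revaccination dose. The two readings differ by the Visit 4 to Visit 5 interval: 30-48 days under Table 4, up to 90 days under Table 8.

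**The case against.** The strongest reply is that no creatinine contrast is planned. Section 4.5.3.1 names rejection, revaccination and HZ episodes, with no non-revaccinated column. The sentence in 4.5 mainly assigns analysis sets. The only post-Visit 3 table that 4.5 names for this group is the "number and percentage of non-revaccinated subjects reporting the occurrence of HZ episodes from visit 3 (Month 24) up to study end" (4.5.3.4). This stands: a reader might infer that the SAP schedules a head-to-head creatinine table, and it does not. What remains is a general statement that the groups are compared, a derivation rule covering exactly that period, and no sentence saying the result is not for comparison.

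Second, the old baseline follows from the design. Non-revaccinated subjects are in an extension of long-term follow-up, and SAP 4.1.2 says: "For the LTFU phase, baseline is latest non-missing pre-primary series dose assessment from ZOSTER-041 study". This also stands. The baseline is coherent as a long-term summary and is not an error in itself.

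Third, the simulated sizes rest on assumptions. Protocol 8.1.9 mandates no test timing and sets recording windows only around rejection, revaccination and HZ, so 12-25 values per non-revaccinated subject cannot be presumed. A reader might infer that the rules necessarily flatter revaccination. The documents do not support that: without drift and with 2-4 values, or with falling creatinine, the non-revaccinated rate is the same or lower.

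Fourth, analyses are descriptive, the allograft-function-after-revaccination endpoint covers revaccinated subjects only, and the higher cut-offs and raw listings are safeguards. All true. They limit the harm, but 1.2-fold is the defined dysfunction threshold.

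**Conclusion.** The two ≥1.2-fold rates would not be comparable, because both baseline and window differ by rule. That conclusion rests on the text and needs no simulation. Its size and direction are unknown: at CV 8% the assumed scenarios run from 0.5% against 9% to 78% against 11% (non-revaccinated against revaccinated). No test, sample-size figure or protocol endpoint uses the non-revaccinated ratio, so the harm is one of interpretation, and the point is worth a wording change.

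The replaced-kidney gap is a smaller part of the same point. The documents do not say that any non-revaccinated subject has a new graft. The Visit 5 label is a separate inconsistency. It affects the window of a stated secondary safety endpoint whether or not the groups are ever compared.

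**What to change.** (a) State in SAP 4.5 and 6.2.3 that the non-revaccinated ratio, from pre-primary baseline to study end, is a separate long-term summary and is not compared with the revaccinated ratio. Flag or exclude subjects with a replacement kidney since ZOSTER-041.

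(b) If any contrast is shown, use the same baseline (3, up to 5, months before Visit 3) and the same post-Visit 3 window in both groups. The window should be no longer than the period for which protocol 8.1.9 requires values in every revaccinated subject included: about 120 days for a 30-day dose interval (30+90). A longer window would go past the required recording for subjects dosed early and make coverage unequal again. Leave the revaccinated endpoint window unchanged. Report the number of baseline and post-baseline values by group. Label the contrast descriptive and confounded by eligibility; a rejection within 90 days, for example, bars revaccination under protocol 6.1.2. Omit it if too few aligned baselines exist.

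(c) Separately, reconcile the Visit 5 (Month 26) label in SAP 6.2.3 and protocol 8.1.9 with dose 2 at Visit 4 (Month 25) and with the endpoint wording.

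Cost: (a) and (c) are SAP wording plus a clarification to protocol 8.1.9; (b) is at most one extra table. Some non-revaccinated subjects may lack recent pre-Visit 3 values, because 8.1.9 requires that recording only around revaccination, rejection or HZ. If too few have them, (a) is enough on comparability.

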6.2.4. Attributing events to vaccine doses

The dose relative to an event is the most recent vaccine dose given to a subject prior to the start of a given event. For example, if the start date of an adverse event is between Dose 1 and Dose 2, the relative dose will be Dose 1.

If an event starts on the same day as a study dose, the relative dose will be derived from the additional information provided in the case report form (CRF) using the contents of the flag indicating if the event occurred before or after study dose. If 'after vaccination' is selected, the relative dose for the event will be the one administered on the start day of the event. If 'vaccination' is selected, the relative dose for the event will be the dose prior to this one.

The number of doses is the number of times the vaccine was administered to a subject

6.2.5. Handling of Missing Data

6.2.5.1. Dates

When partially completed dates (i.e., dates missing a day and/or month) are used in calculations, the following standard rules will be applied:

- A missing day will be replaced by 15
- A missing day and month will be replaced by June 30th.

The following exceptions apply:

When partially completed dates (i.e., with missing day or month) are used in calculations, the following rules will be applied:

- Adverse event start dates with missing day:
 - If the month is not the same as the vaccine dose, then the imputed start date will be the 1st of the month
 - If the event starts in the same month as at least one of the study vaccines, the flag indicating if the event occurred before or after study vaccine (AE.AESTRTPT) will be

used to complete the date. If 'after vaccination' is selected, the imputed start date will match the study vaccine dose given during that month. If 'before vaccination' is selected, the imputed date will be one day before the study vaccine dose given during that month.

- Adverse event start dates with missing day and month:
 - If the year is not the same as the vaccine dose, then the imputed start date will be the 1st of January.
 - If the event starts in the same year as the vaccine dose, the flag indicating if the event occurred before or after vaccination (AE.AESTRPT) will be used to complete the date. If 'after vaccination' is selected, the imputed start date will match the first study vaccine dose given during that year. If 'before vaccination' is selected, the imputed date will be one day before the first study vaccine dose given during that year.
- Adverse event end dates with missing day: the imputed end date will be the last day of the month (30 or 31) or the study conclusion date whichever comes first.
- Adverse event end dates with missing day and month: the imputed end date will be the last day of the year (31st of December) or the study conclusion date whichever comes first.

All incomplete medical history and concomitant medication/vaccination start/end dates will follow the rules above.

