Visit 3 (Month 24) → Visit 4 (Month 25)	30 ^c days	30 - 60
Visit 4 (Month 25) → Visit 5 (Month 26)	30 days	30 - 48
Visit 4 (Month 25) → Visit 6 * (Month 37)	12 months (360 days)	330 - 415
Visit 4 (Month 25) → Visit 7 * (Month 49)	24 months (720 days)	690 - 775

PC 1 = Phone Contact 1

a. Whenever possible the investigator should arrange study visits within this interval.

b. The investigator should endeavour to have the subjects come in for the visits within this interval. However, subjects may not necessarily be excluded from the PPS for analysis of immunogenicity if they make the study visit outside this interval.

c. The second dose will be administered 1 to 2 months (30 to 60 days, inclusive) after the first dose.

* **The allowed interval for Visits 6 and 7 should be the same for both the re-vaccinated and non-revaccinated subjects.**

In times of special circumstances, refer to Section 8.1.16 for allowed interval between study visits.

(Amended: 15 June 2020)

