Code	Condition under which the code is used	Analysis set eliminated from	Visit (timepoints) where the code is applicable	Type of Elimination
	revaccinated without fulfilling the eligibility criteria for revaccination	(revacc. follow-up phase)		
2040	Administration of any concomitant medication(s) forbidden by the protocol	PPS (revacc. active phase), PPS (revacc. follow-up phase)	Visit 1 – Visit 7	Eliminate from Visit(s) only, as applicable
2050	Underlying medical condition forbidden by the protocol, or some Intercurrent medical conditions (IMCs). (To be determined before analysis during data management review (DMR))	PPS (LTFU), PPS (revacc. active phase), PPS (revacc. follow-up phase)	Visit 1 – Visit 7 (visit and onward)	Eliminate from Visit and onwards
2060	Concomitant infection related to the revaccination which may influence immune response – For example, clinically diagnosed suspected HZ cases before Visit 1 or PCR confirmed HZ cases after Visit 1	PPS (LTFU), PPS (revacc. active phase), PPS (revacc. follow-up phase)	Visit 1 – Visit 7	Eliminate from Visit(s) only, as applicable
2070	Concomitant infection not related to the vaccine which may influence immune response – For example, in case of revaccination, any additional confirmed or suspected immunosuppressive or immunodeficient condition (e.g., malignancy, hepatitis, HIV infection, systemic infection)	PPS (LTFU), PPS (revacc. active phase), PPS (revacc. follow-up phase)	Visit 1 – Visit 7	Eliminate from Visit and onwards
2080	Out of window treatment administration – Revaccination dose 1 (study Month 24) to revaccination dose 2 (study Month 25) outside 25-90 day interval	PPS (revacc. active phase), PPS (revacc. follow-up phase)	Visit 3 – Visit 4	Eliminate from Visit and onwards
2090	Missed Visit, excluding phone contact Note: this does not apply to delayed enrolled subjects who had their Visit 1 and Visit 2 on the same day.	PPS (LTFU), PPS (revacc. active phase), PPS (revacc. follow-up phase)	Visit 1 – Visit 7	Eliminate from Visit only
2090	Assessment not properly performed – For example, incomplete assessment, missed assessment except safety follow-up Note: this does not apply to delayed enrolled subjects who had their Visit 1 and Visit 2 on the same day. These subjects would have to have an assessment at either Visit 1 or Visit 2.	PPS (LTFU), PPS (revacc. active phase), PPS (revacc. follow-up phase)	Visit 1 – Visit 7	Eliminate from Visit only

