4.3.2.2. Revaccination phase

The results for the analysis of safety in the revaccination phase will be tabulated as follows:

- Number and percentage of subjects with at least one local AE (solicited and unsolicited), with at least one general AE (solicited and unsolicited), and with any AEs during the solicited 7-day follow-up period will be tabulated with exact 95% CI after each revaccination dose and overall. The same computations will be done for Grade 3 AEs and medically attended AEs. Number and percentage of subjects reporting each individual solicited local AE (any grade and Grade 3) and solicited general AE (any grade, Grade 3, any related and Grade 3 related) during the 7-day follow-up period (i.e., on the day of

[figure not shown]
revaccination and 6 subsequent days) will be tabulated after each revaccination dose and overall.

- Duration of solicited local and solicited general AEs within 7 days and entire duration (lasting longer than 7 days) will be tabulated descriptively overall.
- Number and percentage of subjects with any unsolicited AEs during the 30-day follow-up period (i.e., on the day of revaccination and 29 subsequent days) with its exact 95% CI will be tabulated by MedDRA Primary SOC and PT. Similar tabulations will be done for Grade 3 unsolicited AEs, for any causally related unsolicited AEs, for Grade 3 causally related unsolicited AEs, for Grade 3 non-serious unsolicited AEs, for Grade 3 causally related non-serious unsolicited AEs, non-serious unsolicited AEs, non-serious causally related unsolicited AEs, and for unsolicited AEs resulting in a medically attended visit.
 - The number and percentage doses followed by unsolicited AEs during the 30-day follow-up period with its exact 95% CI will also be tabulated.
- Number and percentage of subjects with at least one report of SAE classified by MedDRA Primary SOC and PT and reported from revaccination Dose 1 up to 30 days post-last revaccination dose, from revaccination Dose 1 up to 12 months post- last revaccination dose, and from revaccination Dose 1 up to study end will be tabulated with exact 95% CI.
- Number and percentage of subjects with at least one report of causally related-SAE classified by MedDRA Primary SOC and PT and reported from revaccination Dose 1 up to 30 days post-last revaccination dose, from revaccination Dose 1 up to 12 months post-last revaccination dose, and from revaccination Dose 1 up to study end will be tabulated with exact 95% CI.

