6.2.6.5. Onset day

The onset day for an event (e.g., AE, concomitant medication/vaccination) is the number of days between the last study dose and the start date of the event. This is 1 for an event occurring on the same day as a study dose (and reported as starting after study dose).

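### When the two revaccination doses are more than 30 days apart, an AE with a missing start day flagged as before Dose 2 is dated into neither 30-day window; at 31 to 59 days this can be wrong

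*SAP*

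**What the plan says.** SAP 6.2.5.1 (Dates) has a branch for AE start dates with a missing day. When the month contains no dose: "If the month is not the same as the vaccine dose, then the imputed start date will be the 1st of the month". When it does contain a dose, a before/after flag decides. An 'after' event takes the dose date. For a 'before' event, "the imputed date will be one day before the study vaccine dose given during that month". The rule does not distinguish Dose 1 from Dose 2.

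Four other provisions determine what follows:

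- **Window.** SAP 4.3.2.2 tabulates unsolicited AEs "during the 30-day follow-up period (i.e., on the day of revaccination and 29 subsequent days".
- **Attribution.** SAP 6.2.4 says that "if the start date of an adverse event is between Dose 1 and Dose 2, the relative dose will be Dose 1". For an event starting on a dose day but flagged as before that dose, "the relative dose for the event will be the dose prior to this one".
- **Onset day.** SAP 6.2.6.5 defines it as the "number of days between the last study dose and the start date of the event", with the dose day counted as Day 1.
- **Dose interval.** Protocol Table 4, footnote c: "The second dose will be administered 1 to 2 months (30 to 60 days, inclusive) after the first dose". Protocol Table 8 extends this to 182 days in special circumstances.

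**The concern.** An event flagged as before Dose 1 is a pre-revaccination event, and dating it to the day before Dose 1 keeps it out of the tables correctly. An event after Dose 1 but before Dose 2 is a post-Dose-1 event. Dating it to the day before Dose 2 places it as far from Dose 1 as it can be. The other missing-day branches choose the earliest possible date (the 1st of the month, or the dose date), so this one leans the opposite way.

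Unsolicited AEs within 30 days of each dose are a secondary safety endpoint, tabulated as any, Grade 3, related, non-serious and medically attended, and also per dose given. The study is small and has no control arm. A non-serious event that leaves the 30-day tables is not picked up by a table covering a continuous period.

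**Working it through.** **Inputs.** Window: dose day plus 29 days (SAP 4.3.2.2). Onset Day 1 = dose day (SAP 6.2.6.5). Let d be the number of days from Dose 1 to Dose 2 and k the day of the month on which Dose 2 is given.

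**The plan's own figure.** 1 + 29 = 30 days, that is onset Days 1 to 30, or 0 to 29 days after the dose. This reproduces.

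**Where the imputed date falls.** Dose 2 minus one day is d − 1 days after Dose 1, which is onset Day d. It is inside the window only if d − 1 ≤ 29, that is d ≤ 30.

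- d = 30: Day 30, inside.
- d = 31: Day 31, outside.

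The date also precedes Dose 2, so it is never in the Dose 2 window. Above 30 days the two doses cannot share a calendar month, so there is no doubt which dose the rule uses.

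**When the exclusion can be wrong.** The earliest possible true onset is the 1st of the Dose 2 month, which is d − (k − 1) days after Dose 1. It lies in the window if d − k + 1 ≤ 29, that is k ≥ d − 28. Since k is at most 31, this needs d ≤ 59. From 60 days no possible onset is in the window and dropping the event is correct.

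**Example.** Dose 1 on 10 June, Dose 2 on 20 July, so d = 40 and k = 20. The possible onsets are 1 to 19 July. Of these, 1 to 9 July are Days 22 to 30, which is k − d + 29 = 20 − 40 + 29 = 9 of 19 days. The rule imputes 19 July, Day 40, and the event is not counted.

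**Enumeration.** Every Dose 1 date over four calendar years was run at each interval from 25 to 182 days, omitting pairs with Dose 2 on the 1st, where no earlier day in that month exists. The imputed date was outside the window for no pair at 25 to 30 days and for every pair at 31 to 182 days. Selected intervals:

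| d (days) | Possible true onset days inside the window | Pairs counted under the rule as written | Pairs counted if the earliest possible date is used |
|---|---|---|---|
| 31 | 93% | 0% | 97% |
| 35 | 69% | 0% | 83% |
| 40 | 44% | 0% | 66% |
| 45 | 25% | 0% | 49% |
| 50 | 11% | 0% | 32% |
| 59 | 0.1% | 0% | 2% |
| 60 and over | 0% | 0% | 0% |

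The second column treats true onsets as spread evenly over the possible days and all Dose 1 calendar dates as equally likely.

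**The case against.** The trigger is narrow. Diary cards cover the 30 days after each dose and are checked with the subject at Visit 4, the Dose 2 visit (Protocol 12.5.9). A wrong exclusion needs a start day still missing after that check, a known month equal to the Dose 2 month, a 'before' flag, a true onset by Day 30 and an interval of 31 to 59 days. At the optimal interval of 30 days the rule works. Percentages are per subject, so a subject with another event in the window still counts in the 'any' row. All of this stands, and it keeps the point minor. It does not make the rule right: just above the optimal interval, most of the possible onset days are inside the window.

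Imputing the earliest date also misplaces some events. In the example, 10 of the 19 possible days are after Day 30 and all 19 would be counted. That is fair: the replacement is the more conservative convention for safety, not an exact correction.

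A reader might infer more than the documents support:

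- **That every exclusion above 30 days is an error.** It can be one only at 31 to 59 days.
- **That such events vanish from the safety report.** SAE, pIMD and biopsy-proven rejection tables run continuously from Dose 1 (SAP 4.3.2.2), and SAP 6.2.4 still assigns the event to Dose 1.
- **That the branch for a missing day and month has the same fault.** It is anchored on the first dose of the year, and the text does not say which dose the flag refers to. Read as before that first dose, an event between the doses is an 'after' event, takes the Dose 1 date and is counted.
- **That the per-protocol interval rule limits the problem.** Elimination code 2080 ("outside 25-90 day interval") applies to the immunogenicity sets, not to the Exposed Set used for these tables.

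**Conclusion.** The point holds for the missing-day branch at Dose 2. At every interval over 30 days the rule removes the event from the 30-day unsolicited AE tables for both doses, although the SAP attributes it to Dose 1. At 31 to 59 days the true onset may have been in the post-Dose-1 window. For these events the rule can only lower the post-Dose-1 rate or leave it unchanged.

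The size of any undercount cannot be computed. The documents give neither the expected number of partial dates, which may be zero, nor the size of the Exposed Set. The 68 subjects in SAP 1.2 are the actual number in the study, not the number revaccinated, so a percentage on that base would not be sound. The effect is probably small and the severity is minor. No immunogenicity endpoint is involved.

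The conclusion assumes that the 30-day tables select events by imputed start date, as SAP 6.2.4 and 6.2.6.5 imply.

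**What to change.** In SAP 6.2.5.1, keep the day-before imputation for events flagged as before Dose 1. For an AE with a missing start day flagged as before Dose 2, impute the later of the 1st of that month and the Dose 1 date. At intervals over 30 days the event is then counted after Dose 1 exactly when at least one of its possible onset days lies in the window. State whether the change also covers medical history and concomitant medication dates, since that section applies the same rules to them.

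The cost is a sentence in the SAP and a small programming change. Some events with true onset after Day 30 will be counted, so unsolicited AE rates may be slightly less favourable. A few may also enter the 7-day tables that combine solicited and unsolicited events. For example, with Dose 1 on 28 June and Dose 2 on 31 July (2 + 31 = 33 days), 1 July is Day 4. A footnote giving the number of AEs with imputed start dates would let readers see how little or how much depends on the rule.
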